For the equity benchmark (overall physical activity program), accessibility and efficacy of the intervention will be compared between the following groups of participants: sex (male; female), race (white; non-white), ethnicity (Hispanic; non-Hispanic), age (continuous/frequency distribution), BMI (continuous/frequency distribution), income ($\leq \$44,999$; $\$45,000$ to $\$84,999$; $\$85,000$ to $\$124,999$; $\geq \$125,000$), able-bodied (continuous/frequency distribution of total constraints and total difficulties with mobility). It should be noted that the Formative Study is not statistically powered to compare groups of subjects, so these between-group comparisons will be a subjective examination of System Usability Scale scores (for accessibility) and reported change/lack of change in physical activity enjoyment (for efficacy) across all levels of each of the sub-groups. If these values are approximately equal between the groups, then the benchmark will be achieved. Even though statistical testing will not be performed for this benchmark due to a lack of power, we will report raw tallied data to promote transparency.

For the Psychological Needs Component's accessibility/usability benchmark, the total number of self-reported physical activity type, location, and listening context constraints are tallied for each person. Cross-tabulation tables will then allow for the reported ability to follow activity recommendations (yes/no) to be qualitatively compared across the full range of total constraints (physical activity type, location, and listening context) reported by all participants. To achieve the benchmark, there must not be an observable trend between the number of constraints reported and a person's ability to follow the activity recommendations (e.g., when the cross-tabulation table is studied, participants in the upper half of the distribution for total constraints should be, at the very least, approximately equally as heterogenous as the lower half of the distribution for reported ability to engage [yes/no] in the activity recommendations). As above, the raw tallied data will be reported to promote transparency.

Comparison Study

Exploratory analysis will examine the distributions, identify needed data transformations, investigate multicollinearity, and identify extreme observations. Data will be analyzed with SAS and R. Missing data analyses will involve considerations of imputation methods,^{93,94} attrition propensity scores⁹⁵ based on the compliance/dropout for each participant,⁹⁶ and sensitivity analyses. We will consider age, sex, income, Version 04.02.25

race/ethnicity, BMI, and fitness as confounders. Other variables associated with outcomes ($p < .10$) will be included as covariates. Exploratory tests of moderation will also be conducted, as there may be sex and age differences in physical activity^{97,98} and affective mechanisms.^{99–101} Power estimates were evaluated using Monte Carlo simulations in Mplus.^{102–105} The estimated effect size of affect-based physical activity interventions range from a small effect on the primary outcome (affective response) ($f^2 = 0.04$, representing a 0.3 point increase on a 5-point affect scale)⁵⁴ to a medium effect on the secondary outcome (physical activity) ($f^2 = 0.17$, representing a 30/min week increase in MVPA).¹⁰⁶ A sample of $N=200$ participants (100 per condition) (after ~30% attrition) is needed to detect small between-subject effects on change in the outcomes (H2 and H3) with $\beta = .80$ and $\alpha = .05$. To detect within-subject effects (H1 and H4), our level-1 sample sizes will be much larger (e.g., $200 \times 4 \times 4 \times 7$ level-1 N for daily data). Thus, we should have sufficient power to detect very small effects for the remaining associations. H5 is exploratory and not statistically powered.

AIM 1: Determine whether affective mechanisms can be experimentally manipulated. In the Formative study, descriptive statistics (means, frequencies) will assess acceptability and feasibility of content, delivery methods, device usage, engagement, and raw values for change in affective mechanisms. The Comparison study will use an “intent to treat” approach to test the (1) within-subject effects of affect- vs. intensity-based goals (H1), (2) between-subject effects of affect-based goals with vs. without TYPE/CONTEXT (H2), and (3) between-subject effects of affect-based goals with vs. without SAVOR (H3) on the primary outcome (affective responses and affectively-charged motivations) and secondary outcome (physical activity). We will use random-effect regression models (level 1-days, level 2-subjects), which adjust for clustering within subjects and incorporate random effects.¹⁰⁷ Each treatment effect and each outcome will be tested in separate models. We will examine cross-level interactions between affect-based goals with vs. without savoring (level 2) and affective responses (level 1) to test H3.

AIM 2: Determine whether affective mechanisms mediate effects of interventions on physical activity (Comparison Study). Multilevel mediation will be tested using a 1-1-1 strategy that fits a set of simultaneous equations using path analysis in R.¹⁰⁸ Analyses will test the effects of intervention engagement on same-day/same-week affectively-charged motivations and affective response; the effects of affectively-charged motivations on same-day/same-week physical activity and the effects of affective responses on next-day/next-week physical activity; the indirect effects of intervention engagement on same- and next-day/same- and next-week physical activity via affective mechanisms (H4); and the total effects (mediated plus unmediated) of intervention engagement on physical activity.

AIM 3: Explore cross-person and cross-situation moderating effects (Comparison study). We will add interaction terms for time-varying and time-invariant effect moderators (H5).¹⁰⁹

Dissemination of Findings

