
5. Methods

Procedures

Both the Formative and Comparison Studies will follow the general procedures outlined in Table 1.

Consent. Participants provide informed consent during a scheduled private video conference with a trained study team member.

Table 1. Study Procedures

Start-Up	Onboarding	Intervention	Exit
Informed Consent	Orientation	Morning/Evening Goal Sessions	Post-Study Questionnaire
Baseline Questionnaire	Random Assignment ^a	Wear Fitbit	Exit Interview ^b
Morning/Evening Goal Sessions ("Text Messages")	Run-In Period	EMA ("Check-Ins")	
Mail Fitbit & Instructions		Mid-Study Questionnaire ^a	
		Implicit Associations Test (IAT) ^a	

Note. ^a Comparison Study only; ^b Formative Study only.

Baseline Questionnaire. Following informed consent, participants receive an email with a link to a 45-minute HIPAA-compliant REDCap baseline questionnaire. This survey measures self-regulatory capacity (self-control, intentions, self-efficacy) and importance of psychological needs; sociodemographic, anthropometric (self-reported height and weight), personality, mental health, physical activity information, and participants' addresses will also be collected. If participants indicate that they complete more than 800 minutes of MVPA or greater than 60 minutes of vigorous physical activity on the baseline questionnaire, they can be found ineligible and be removed the study.

Morning/Evening Goal Sessions ("text messages"). Following the baseline questionnaire, participants are asked to complete ≤ 3 days of morning and evening goal sessions ("text messages"). These sessions include seven affect items and include a question at the end asking, "Do you think you could answer a survey like this most morning and evenings for 19 weeks?". The study team will use this as a brief check before sending participants a Fitbit Versa smartwatch.

Mail Fitbit and Instructions. The study staff then mail a Fitbit Versa smartwatch with instructions to each participant.

Table 1. Study Procedures

Start-Up	Onboarding	Intervention	Exit
Informed Consent	Orientation	Morning/Evening Goal Sessions	Post-Study Questionnaire
Baseline Questionnaire	Random Assignment ^a	Wear Fitbit	Exit Interview ^b
Morning/Evening Goal Sessions ("Text Messages")	Run-In Period	EMA ("Check-Ins")	
Mail Fitbit & Instructions		Mid-Study Questionnaire ^a	
		Implicit Associations Test (IAT) ^a	

Note. ^a Comparison Study only; ^b Formative Study only.

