The 19-week Comparison study (N=360) will then use a Multiphase Optimization Strategy (MOST) design to determine the effects of each intervention component.^{37,38} Specifically, we will compare affect- and intensity-based goals within-persons and affect-based goal condition enhancements between-persons (Figure 1). Participants are randomly assigned to treatment groups. The study protocol begins with a run-in period (described above), followed by either affect- or intensity-based goals for the first 8-weeks, a two week washout period, and a cross-over to receive the alternate condition for the remaining 8-weeks. During the affect-based goal condition, participants also randomly receive one of four possible combinations of TYPE/CONTEXT and SAVOR enhancements: [1] affect-based goal setting alone; [2] affect-based goals + TYPE/CONTEXT; [3] affect-based goals + SAVOR, [4] affect-based goal setting + TYPE/CONTEXT + SAVOR.

Figure 1. Comparison Study Design

Note. ^a Brief savoring experiences; ^b Tailored recommendations for activity types and contexts to satisfy important psychological needs.

Intervention

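### Affect measured before any enhancement begins is already collected, but no H2 or H3 model names it as a covariate or as the reference for change

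*Combined protocol and SAP*

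**What the plan says.** **Start-up ratings.** The protocol (5. Methods, Procedures, Morning/Evening Goal Sessions) asks every participant for up to 3 days of sessions after the baseline questionnaire. "These sessions include seven affect items", and a closing question asks whether the participant could keep answering for 19 weeks. The stated use is: "The study team will use this as a brief check before sending participants a Fitbit Versa smartwatch". Table 1 places these sessions in Start-Up, ahead of Random Assignment.

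**Intensity phase.** There are eight groups of 45, and four of them take the intensity-based phase first (Random Assignment). The design description says: "During the affect-based goal condition, participants also randomly receive one of four possible combinations of TYPE/CONTEXT and SAVOR enhancements". Intensity-first participants therefore complete 8 weeks and a 2-week washout before any enhancement. Instrumentation schedules activity-triggered ratings and morning motivation items in the Comparison Study and does not restrict them to one phase.

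**Analysis.** Data Analysis, Comparison Study, lists age, sex, income, "race/ethnicity, BMI, and fitness as confounders". Any other variable enters if it is associated with the outcome at p < .10, and no candidate list is given. Under Aim 1, H2 and H3 are tested in random-effect regressions of days within subjects, one model per effect and outcome, with no baseline affect term. The power statement says that the sample "is needed to detect small between-subject effects on change in the outcomes (H2 and H3"). No affect reference for that change is named. The run-in baseline is physical activity.

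**The concern.** H2 and the mean effects of SAVOR are comparisons between people. Stable differences in how people rate affect add directly to the error of such a comparison, and a pre-treatment measure of the same or a related quantity can remove part of it. Here such measures exist for everyone (start-up ratings) and, in a closer form, for half the sample (intensity phase).

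The plan leaves their use open. Start-up affect could enter only through a screen that depends on the outcome data. The intensity phase is not mentioned as a reference at all, although the power statement speaks of change. At stake are the width of the intervals for the two enhancement effects on the primary outcomes, and one analyst choice that could be closed in advance. Validity is not at stake, because assignment is randomised.

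**Working it through.** **Inputs from the documents** (Data Analysis, Comparison Study, unless noted)
- Effect: "primary outcome (affective response) ($f^2 = 0.04$, representing a 0.3 point increase on a 5-point affect scale".
- Error rates: "with $\beta = .80$ and $\alpha = .05". I read .80 as power and alpha as two-sided, since sidedness is not stated.
- Sample: "A sample of $N=200$ participants (100 per condition) (after ~30% attrition").
- 8 × 45 = 360 randomised (Random Assignment). With 30% attrition, 360 × 0.70 = 252 remain, or 126 v 126 for each enhancement.

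**Assumption.** The correlation r between a pre-enhancement measure and the affect-phase outcome is not in the documents. I show it from 0 upwards.

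**Step 1. Reproduce the plan's N.** For two equal groups d = 2√f² = 2√0.04 = 0.40, which with a 0.3-point shift implies SD = 0.3/0.40 = 0.75. The normal formula gives 99 per arm (198 in all). The exact F test with 1 df gives N = 199, and power at N = 200 is .804. The stated 200 is reproduced. This is a closed-form check, because the inputs to the Mplus simulation are not reported.

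**Step 2. Power at the expected number of completers.** At N = 252 with no covariate, exact F power is .885.

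**Step 3. Start-up affect as a covariate for everyone.** Residual variance falls by the factor 1 − r², so information rises by 1/(1 − r²). If f² = 0.04 refers to unadjusted variance, it becomes 0.04/(1 − r²).

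| r | Information | 252 act like | Power at N = 200 |
|---|---|---|---|
| 0 | 1.00 | 252 | .804 |
| .2 | 1.04 | 262 | .819 |
| .3 | 1.10 | 277 | .839 |
| .5 | 1.33 | 336 | .901 |

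**Step 4. Intensity-phase mean in the Intensity-first half only.** Pooling the two order strata by inverse variance gives information [1/(1 − r²) + 1]/2.

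| r | Information | 252 act like |
|---|---|---|
| 0 | 1.00 | 252 |
| .5 | 1.17 | 294 |
| .6 | 1.28 | 323 |
| .7 | 1.48 | 373 |

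**Step 5. Both together.** Take r = .3 in the Affect-first half and a total r of .5, .6 or .7 in the Intensity-first half. Power at N = 200 (normal formula) is .877, .904 or .938.

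**Step 6. What a change score would imply.** If d = 0.40 is on the raw SD and a simple change score is analysed, its variance is 2(1 − r) times the raw variance. The N required is then 394 at r = 0, 276 at r = .3, 198 at r = .5 and 118 at r = .7. The stated N = 200 therefore fits either a post-only comparison or a change score with r near .5. The documents do not say which, so the gains in Step 3 hold only if 0.04 is on unadjusted variance.

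**The case against.** **The screen might admit start-up affect anyway.** A reader might infer that the plan excludes these data. It does not. If r were .3 and start-up affect were tested at N = 200, Fisher z would be atanh(.3) × √197 ≈ 4.3 against a cut-off of 1.645, and it would enter with probability above .99. So the accurate statement is that no model names these data. What survives is that the candidate list is undefined and the choice depends on the outcome.

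**Change may already imply a reference.** The power statement may have some pre-enhancement measure in mind, and Aim 1 does not say that intensity-phase days are dropped from H2 and H3. This stands, and is a reason to name the reference. It also means that part of the gain in Step 3 may already be counted in f² = 0.04.

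**The correlations may be low.** Instrumentation describes the morning-session items as incidental affect. Start-up ratings are therefore probably not affective response during activity and not the motivation item, and they cover at most 3 days. The intensity phase matches the instruments, but under a different, progressively harder condition. Both points stand, and are why the ranges start at 0. Instrumentation also labels some baseline questionnaire scales, including affective motivation, as covariates without placing them in a model. If those entered, the added gain would be smaller.

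**H3's distinctive test does not benefit directly.** H3 rests on a cross-level interaction, that is, a difference in slopes. A baseline mean does not directly sharpen it. This stands, and the point is limited to mean contrasts.

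**The trial has power enough.** A reader might infer that the omission leaves H2 and H3 underpowered or biased. Neither follows: power is about .89 at 252 completers with no covariate, and randomisation protects against bias.

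**Conclusion.** The point holds as a low-cost gain in precision for the mean contrasts on affective response and motivation: H2 and the mean effects of SAVOR. Two pre-enhancement sources exist, no H2 or H3 model names either, and the power statement refers to change without an affect reference.

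The size cannot be fixed from the documents. It runs from nothing to 33% more information for start-up affect (r = 0 to .5), and from nothing to 48% for the intensity-phase mean in half the sample (r = 0 to .7). In power terms, start-up affect takes .80 at N = 200 to at most about .90. At the expected 252 completers the trial already meets its target, so the benefit is narrower intervals and some protection if the effect is smaller than planned. For example, at an illustrative f² = 0.03 and N = 252, power moves from .78 to .82 (r = .3) or .89 (r = .5).

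These figures assume that f² = 0.04 is on unadjusted variance and that about 30% are lost. They also assume that Intensity-first participants receive no enhancement content before their affect phase, as the design description states.

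**What to change.** In the SAP, for the models of mean affective response and mean affectively charged motivation (H2 and the mean SAVOR effects):

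1. Include the person-mean of the seven start-up items as a fixed covariate, whatever the p < .10 screen shows.
2. Include a term for order (Intensity-first or Affect-first).
3. For Intensity-first participants only, add the intensity-phase person mean of the same outcome, nested in order and held constant for Affect-first participants. Do not use the Affect-first intensity phase as a baseline, because it follows the enhancement and could carry part of its effect.
4. For a missing baseline value, use the mean plus a missing indicator.
5. State the reference for change in H2 and H3, and whether f² = 0.04 is on unadjusted or residual variance.

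Leave the H3 cross-level interaction as planned, and claim no gain for it from these terms. The cost is SAP wording, two covariates beside the order term, and the missing-value rule. It adds no data collection and no burden on participants. The wording should be fixed before outcome data are examined.

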Orientation. Once study materials are received, the participant attends a remote orientation session where they will be introduced to the study and watch a summary presentation with instructions on how to participate. During this session, participants are led through setting up their smartphone and Fitbit Versa smartwatch to our study platform through Fitabase, to allow for tracking of physical activity and delivery of EMA ("check-ins"); study staff then teach them how to complete smartphone based morning and evening goal sessions and how to respond to EMA ("check-ins") on their Fitbit smartwatch.

Random Assignment. Random assignment will be stratified by sex at birth and assigned using the randomization allocation table via REDCap. Participants will be assigned to one of eight groups (n=45 each), based on order and intervention components: Intensity > Affect (No Enhancements), Intensity > Affect (Tailored Recommendations), Intensity > Affect (Savoring), Intensity > Affect (Tailored Recommendations & Savoring), Affect (No Enhancements) > Intensity, Affect (Tailored Recommendations) > Intensity, Affect (Savoring) > Intensity, Affect (Tailored Recommendations & Savoring) > Intensity.

[figure not shown]
Run-in Period. The Comparison Study will begin with a week-long Fitbit smartwatch assessment-only run-in period to introduce participants to wearing and charging the Fitbit smartwatch and collect baseline physical activity data.

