Intervention Period. The 19 weeks of study participation for the Comparison Study and three weeks for the Formative Study officially “start” on the first day of the run-in period. While everyone receives physical activity prescriptions, treatment delivery varies by group assignment (affect- or intensity-based goal setting), which is randomized for the Comparison Study. Morning and evening goal sessions, Fitbit wearing, and EMA (“check-in”) procedures are described in the Intervention and Instrumentation sections below. During the morning goal sessions, they also will complete a mobile Implicit Associations Tests (IAT) (i.e., called a “smartphone word match activity”) (for the sub-sample recruited to the Comparison Study n=120). Participants in the Comparison Study will additionally respond to a Mid-Study Questionnaire halfway through the study. Upon study completion, participants are asked to fill out a 30-minute REDCap questionnaire, with Formative Study and participants in the Comparison Study subsample recruited starting March 2025 (n=120) additionally completing an open-ended qualitative exit interview. The consent, orientation, and exit interview remote sessions are all scheduled by the participant using a Calendly integration. Periodic emails and text messages will also be sent to encourage study participants’ progress every few weeks.

The three-week Formative study (N=56) will iteratively test and refine the implementation of a novel treatment to manipulate affective mechanisms during physical activity. Acceptability and feasibility of content, delivery, device usage, engagement, and achieving clinically meaningful changes in affective mechanisms will be addressed.³⁶ Treatment components targeting intensity-based goals and affect-based goals will be tested separately in four groups of n=14 participants: [1] intensity-based goal setting alone; [2] affect-based goals + TYPE/CONTEXT; [3] affect-based goals + SAVOR; [4] affect-based goals + TYPE/CONTEXT + SAVOR. Testing occurs on a rolling basis with 1–2-week gaps to allow for iterative refinements.

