For the Comparison Study, participants will receive four payments of up to \$100 each (paid every 4 weeks): \$50 for wearing the Fitbit Versa smartwatch all day and night (≥ 23 h/day) and \$50 for answering all smartwatch EMA (“check-ins”; except for those that occur while driving, sleeping, or another activity that precludes responding). A \$50 payment will also be given during the 2-week “washout” break for wearing the Fitbit Versa smartwatch all day and night (≥ 23 h/day), and another \$50 payment will be given for completing the Baseline (\$20), Mid-Study (\$15), and Post-Study Questionnaire (\$15) s. The total possible compensation for the 19-week Comparison Study is \$500, and participants also keep the Fitbit Versa smartwatch upon completion. For the 120 participants in the Comparison Study sub-sample (recruited starting March 2025), the compensation structure will be the same, except they will instead receive four payments of up to \$120 each (paid every 4 weeks): \$60 for wearing the Fitbit Versa smartwatch all day and night (≥ 23 h/day) and \$60 for answering all smartwatch EMA (“check-ins”; except for those that occur while driving, sleeping, or another activity that precludes responding), and \$20 for completing an exit interview, for a total of \$600.

Participant Privacy & Data Management

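### No pre-treatment measurement of the primary affect outcomes is scheduled, yet H2 and H3 are powered on change; the contrast needs defining, and affect baselines already collected should be used

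*Combined protocol and SAP*

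**What the plan says.** All references are to the combined protocol and SAP.

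- **Methods, Run-in Period.** The Comparison Study opens with a week-long "Fitbit smartwatch assessment-only run-in period to introduce participants to wearing and charging the Fitbit smartwatch and collect baseline physical activity data". Affect is not mentioned.
- **Methods, Intervention Period.** The 19 weeks are counted from "on the first day of the run-in period". Whether EMA is active in that first week is not stated.
- **Instrumentation.** Affective response is captured by event-contingent EMA when the watch detects activity. Affectively-charged motivation is one AFFEXX item in the morning goal session. A separate evening check-in goes out daily at 8 pm and asks about affect over the whole day.
- **Methods, start-up steps.** Before the watch is mailed, participants complete up to three days of morning and evening sessions carrying seven affect items. The only stated use is a check before mailing.
- **Baseline Questionnaire.** It includes affective motivation for, and enjoyment of, physical activity.
- **Data Analysis, Comparison Study (power).** The plan assumes a "small effect on the primary outcome (affective response) ($f^2 = 0.04$, representing a 0.3 point increase on a 5-point affect scale"), and states that 200 "participants (100 per condition) (after ~30% attrition) is needed" for effects "on change" only in the sense of this clause: the sample "is needed to detect small between-subject effects on change in the outcomes (H2 and H3").
- **Data Analysis, Aim 1.** H1 to H3 are tested "on the primary outcome (affective responses and affectively-charged motivations) and secondary outcome (physical activity") with day-level random-effects regression. No baseline term and no change score is named.

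**The concern.** The secondary outcome, physical activity, has an explicit baseline week. The primary outcome has none that the plan specifies, although the power statement speaks of change. Three things are at stake.

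First, the reader cannot tell what H2 and H3 estimate for affect. It could be change from a pre-treatment value, the difference between the two phases, a trend within the affect phase, or simply the level in the affect phase. The power statement points to one of the first three, while the model description reads as the last.

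Second, people differ in a stable way in how they rate affect. A between-person comparison of levels carries all of that variation, and a baseline covariate would remove part of it.

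Third, the natural substitute baseline, the intensity phase, comes before the enhancement only in the Intensity-first groups. In the four Affect-first groups (4 × 45 = 180 of 360 people) it comes after.

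**Working it through.** **1. What is measured before treatment**

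| Measure | Scheduled before treatment? | Section |
|---|---|---|
| Physical activity (secondary outcome) | Yes, in the run-in | Run-in Period |
| In-activity affective response (primary) | Not specified | Instrumentation |
| AFFEXX motivation item (primary) | Not specified | Instrumentation |
| Evening whole-day affect | Not specified for the run-in | Instrumentation |
| Seven general affect items | Yes, up to 3 days at start-up | Methods, start-up |
| Affective motivation, enjoyment | Yes | Baseline Questionnaire |

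**2. Reproducing N = 200**

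Inputs from the power paragraph: f² = 0.04, α = 0.05 (two-sided assumed) and power 0.80 (printed there as β = .80).

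- d = 2√f² = 2√0.04 = 0.40. A 0.3-point difference then implies SD = 0.3/0.40 = 0.75.
- Normal approximation: n per arm = 2(1.960 + 0.842)²/0.40² = 98.1, so 99 per arm and 198 in total.
- Noncentral F with 1 numerator df: N = 199 reaches 0.80, and power at N = 200 is 0.804.

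The stated 200 is reproduced by a plain two-group comparison with no baseline. These closed forms stand in for the Mplus simulation, whose inputs the plan does not give.

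**3. What a baseline covariate would add**

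Assume f² = 0.04 is on the outcome's own variance and a baseline has correlation r with the affect-phase mean. Then adjusted f² = 0.04/(1 − r²), noncentrality λ = 200 × adjusted f², and the equivalent unadjusted N is 200/(1 − r²). The documents give no r, so a range is shown.

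| r (assumed) | Adjusted f² | λ | Power at N = 200 | Equivalent N |
|---|---|---|---|---|
| 0 | 0.040 | 8.00 | 0.80 | 200 |
| 0.3 | 0.044 | 8.79 | 0.84 | 220 |
| 0.5 | 0.053 | 10.67 | 0.90 | 267 |
| 0.6 | 0.0625 | 12.50 | 0.94 | 312 |

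**4. If f² was instead standardised to change**

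With equal variances, the standardised effect on levels is 0.40 × √(2(1 − r)). For 100 per arm, analysed on levels without a baseline:

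- r = 0.3: d = 0.473, power 0.92
- r = 0.5: d = 0.400, power 0.81
- r = 0.6: d = 0.358, power 0.72
- r = 0.7: d = 0.310, power 0.59

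Under this reading the missing baseline costs power only when r exceeds 0.5. The plan does not say which reading applies.

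**5. The phase difference as a substitute**

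Affect phase minus intensity phase exists for everyone who completes both. Let δ be the enhancement effect and suppose a fraction k of it persists into a later intensity phase. The contrast is δ in Intensity-first groups and δ(1 − k) in Affect-first groups. With equal halves the pooled value is δ(1 − k/2), so an assumed k = 0.25 shrinks it by 12.5%.

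**The case against.** A reader might infer that the run-in records no affect at all, that no pre-treatment affect exists, and that change therefore cannot be formed. The documents do not support any of these.

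- **EMA in the run-in is unspecified, not excluded.** Evening check-ins are daily, the study clock starts at the run-in, and EMA is taught at orientation beforehand. Table 1 lists EMA under Intervention, but it lists Fitbit wear there too, and the watch is certainly worn in the run-in. The EMA payments span 4 × 4 = 16 weeks and the washout payment covers only the "break for wearing the Fitbit Versa smartwatch all day and night". But no run-in payment is listed for wear either, so the payment schedule settles nothing about that week.
- **Affect-related baselines exist.** They are the start-up items and the questionnaire scores. They are not the primary measures, and the analysis section gives them no role, but they can serve as covariates.
- **Change can be formed across phases**, or as a trend over the 8 weeks. The carryover risk in step 5 is a weakness of the phase difference, not a bar to it.
- **H2 and H3 are randomised contrasts**, valid on affect-phase levels, and N = 200 gives the planned power that way. With 360 less 30% = 252 analysed, unadjusted power is about 0.89.
- **First-use effects** of rating affect on the watch are balanced across randomised enhancement groups and do not bias H2 or H3.
- **Part of the gain may already be available**, since the plan admits covariates associated with outcomes at p < .10. That depends on a data-driven screen, and the plan does not say that the affect baselines would be entered into it.
- **H3's affect hypothesis is a cross-level interaction.** The mean-level figures above do not describe its power.

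All of this stands. What remains is that the power statement and the models describe different things, and that a cheap source of precision is not pre-specified.

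**Conclusion.** The point holds as a gap in specification and precision. The plan schedules no pre-treatment value of either primary affect measure, powers H2 and H3 on an undefined change, and fits models without a baseline. It does not follow that H2 or H3 is biased or untestable.

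The size is a possible rise in power from 0.80 to between 0.84 and 0.94 at N = 200. This rests on assumed correlations of 0.3 to 0.6 and on f² = 0.04 referring to the outcome's own variance. General affect or questionnaire motivation may correlate less with the primary measures than the same measure would, so the lower end is the cautious expectation. If f² refers to change, an analysis of levels at N = 200 is underpowered for r above 0.5 (0.72 at 0.6, 0.59 at 0.7), which is why the contrast behind the effect size must be stated.

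**What to change.** 1. **Pre-specify baseline covariates in the H2 and H3 models**, in place of the p < .10 screen for these variables. Use the per-person mean of the seven start-up affect items for affective response, and the Baseline Questionnaire affective motivation score for affectively-charged motivation. These data are already collected, so the cost is an edit to the analysis section.
2. **For participants not yet enrolled**, run the existing evening check-in during the run-in, ask the AFFEXX item in the start-up sessions, and use these as the baseline covariates. State in the Run-in Period text which check-ins are active. The cost is a short amendment, one more week of roughly 30-second check-ins, and a baseline of mixed type across the cohort. An indicator for baseline type, with its interaction with the baseline value, would handle the mixture. Event-contingent prompts in the run-in are optional: in inactive adults they may be sparse, and they could influence the baseline activity being measured.
3. **Reword the power statement** so that H2 and H3 are powered on baseline-adjusted affect-phase levels instead of change, and say that f² = 0.04 refers to that contrast. If the phase difference is reported as well, label it secondary and note the possible carryover in the Affect-first groups.
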